9.8.2. Time-to-Response

Time-to-response (for responders only, per IMWG criteria) is calculated as the time from the first date of dosing of study treatment to the first date of documented response (PR or better).

Time-to-response will be summarized using descriptive statistics or listed by dose cohort and arm.

9.8.3. **Duration of Response**

Duration of response (for responders only, per IMWG criteria) is defined as time from the earliest date of documented response (PR or better) to the earliest date when disease progression was confirmed. Duration of response will be summarized using Kaplan Meier statistics as appropriate or listed by dose cohort and arm.

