2. STUDY OBJECTIVES AND ENDPOINTS

Table 1: Study Objectives

Primary Objective

The primary objective of the study is to determine the safety and efficacy of D^2 in subjects with RRMM.

Secondary Objectives

The secondary objectives are:

- Evaluate additional measures of efficacy of D² in subjects with RRMM
- Evaluate the pharmacokinetics (PK) of DURVA and DARA in subjects with RRMM

[figure not shown]

Table 2: Study Endpoints

Endpoint	Name	Description
Primary	Overall response rate (ORR)	Tumor response, including progressive disease (PD) according to the International Myeloma Working Group (IMWG) Uniform Response Criteria (Rajkumar, 2011).
Primary	Safety	Type, frequency, seriousness and severity of adverse events (AEs), and relationship of AEs to study treatment
Secondary	Time-to-response (TTR)	Time from enrollment to the first documentation of response (Partial Response [PR] or greater)
Secondary	Duration of response (DOR)	Time from the first documentation of response (PR or greater) to the first documentation of PD

Table 2: Study Endpoints (Continued)

Endpoint	Name	Description
Secondary	Progression-free survival (PFS)	Time from enrollment to the first documentation of PD or death from any cause during study, whichever occurs earlier
Secondary	PK parameters	Typical serum/plasma PK parameters for DURVA and DARA, such as maximum observed concentration (C_{max}) area under the concentration-time curve (AUC), time to maximum concentration (T_{max}), terminal elimination half-life ($t_{1/2}$), clearance (CL/F), and volume of distribution (V_z /F)

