6.2.1. End of Treatment

An End of Treatment (EOT) evaluation will be performed for subjects who are withdrawn from treatment for any reason within 7 days after the decision to permanently discontinue treatment has been made.

The following evaluations will be performed as specified in Table 4.

- IRT registration
- Concomitant medications evaluation (monitored until 90 days after last dose of DURVA or DARA, whichever is later)
- Concomitant procedures evaluation (monitored until 90 days after last dose of DURVA or DARA, whichever is later)
- Adverse event evaluation (monitored until 90 days after last dose of DURVA or DARA, whichever is later)

- SPM monitoring for subjects who received POM as part of study treatment (monitored until the last subject completes the 90 day follow-up visit)
- Physical examination, including assessment for potential VTEs (can be source-documented only)
- Vital signs
- Weight
- 12-lead ECG
- Hematology panel
- Coagulation parameters
- Chemistry panel
- Thyroid function tests (TSH, free T₄, free T₃)
- Renal function (CrCl)
- Urinalysis
- Urine (or serum) pregnancy test for FCBP
- Counseling about pregnancy precautions and the potential risks of fetal exposure for subjects receiving POM
- ECOG Performance Status
- Efficacy assessments will be performed according to the schedule defined in the Table of Events and do not need to be performed specifically for the EOT visit except as specified in Section 6.4.
- Beta-2 microglobulin test
- Blood sampling for PK assessments (see Section 6.5)
- Study treatment (durvalumab, daratumumab, POM, or dex) accountability/compliance.

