6.4. Efficacy Assessments

6.4.1. Laboratory Assessments for Efficacy Parameters

All laboratory assessments for efficacy will be performed centrally.

If screening assessments are performed within 3 days of C1D1, efficacy laboratory assessments need not be repeated at C1D1:

- Serum protein electrophoresis (sPEP) and urine protein electrophoresis (uPEP) tests (performed on 24-hour urine collection) are required at screening, on Day 1 of each cycle, and at the EOT Visit.
- Serum and urine immunofixation tests are required at screening, on Day 1 of each cycle, and at the EOT Visit.

- Quantitative serum immunoglobulin assessment includes IgG, IgA, and IgM for all subjects, and IgE or IgD only for subjects with the respective MM sub-type (IgE or IgD) and is required at screening, on Day 1 of each cycle, and at the EOT Visit.
- Serum free light chains assay is required at screening, on Day 1 of each cycle, and at the EOT Visit.
- Corrected serum calcium will be assessed as part of the safety serum chemistry assessments performed at screening, on Day 1 of each cycle, and at the EOT Visit.

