6.4.5. Assessment of Response

Starting from Cycle 2, response will be assessed by the investigators using the International Myeloma Working Group (IMWG) Uniform Response Criteria (Rajkumar, 2011) (Appendix B) at every cycle on Day 1 and at the EOT Visit. Response must be based on the central laboratory data to ensure consistency across investigative sites.

NOTE: Per IMWG Uniform Response Criteria all response categories and progressive disease require 2 consecutive assessments except for radiographic or bone marrow assessments

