9.8.4. Progression-free survival (PFS)

Progression-free survival will be calculated as the time between the enrollment and PD, as determined by the investigator using the IMWG criteria, or death, whichever occurred earlier. Subjects who do not have a PFS event will be censored on the last adequate response assessment date. Progression-free survival will be summarized for full analysis population using Kaplan-Meier statistics as appropriate or listed by dose cohort and arm.

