	Only in patients without measurable serum and urine M protein levels and without measurable disease by FLC levels, bone marrow plasma cell percentage (absolute percentage must be $\geq 10\%$)	
	Definite development of new bone lesions or soft tissue plasmacytomas or definite increase in the size of existing bone lesions or soft tissue plasmacytomas	
	Development of hypercalcemia (corrected serum calcium > 11.5 mg/dL) that can be attributed solely to the plasma cell proliferative disorder	
Additional Response Crite	eria	
Molecular Complete Response	CR plus negative allele-specific oligonucleotide polymerase chain reaction (ASO-PCR), sensitivity 10 ⁻⁵	
Immunophenotypic	Stringent CR plus	
Complete Response	Absence of phenotypically aberrant plasma cells (clonal) in BM with a minimum of 1 million total BM cells analyzed by multiparametric flow cytometry (with > 4 colors)	
Minimal Response (MR)	≥ 25% but ≤ 49% reduction of serum M-protein and reduction in 24-hour urine M-protein by 50%-89%	
in patients with relapsed refractory myeloma adopted from the European Group for Blood and	In addition to the above criteria, if present at baseline, 25%-49% reduction in the size of soft tissue plasmacytomas is also required	
Marrow Transplantation (EBMT) criteria	No increase in size or number of lytic bone lesions (development of compression fracture does not exclude response)	

a All response categories (CR, sCR, VGPR, PR, and PD) require 2 consecutive assessments made at any time before the institution of any new therapy; CR, sCR, VGPR, PR, and SD categories also require no known evidence of progressive or new bone lesions if radiographic studies were performed. VGPR and CR categories require serum and urine studies regardless of whether disease at baseline was measurable on serum, urine, both, or neither. Radiographic studies are not required to satisfy these response requirements. Bone marrow assessments need not be confirmed. For PD, serum M-component increases of more than or equal to 1 g/dL are sufficient to define relapse if the starting M-component is ≥ 5 g/dL.

Source: Rajkumar, 2011

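### Read literally, Section 9.8.3 ends duration of response when PD is confirmed, while Table 2 ends it when PD is first documented; for laboratory PD the dates can differ, nominally by 28 days

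*Combined protocol and SAP*

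**What the plan says.** DOR is defined twice. Table 2 in Section 2 gives "Time from the first documentation of response (PR or greater) to the first documentation of PD". Section 9.8.3 gives "time from the earliest date of documented response (PR or better) to the earliest date when disease progression was confirmed".

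PFS is also defined twice. Table 2 gives "Time from enrollment to the first documentation of PD or death from any cause during study, whichever occurs earlier". Section 9.8.4 refers only to "PD, as determined by the investigator using the IMWG criteria", or death, and does not say which date counts when PD rests on two assessments.

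The confirmation rule is in Section 6.4.5: "all response categories and progressive disease require 2 consecutive assessments except for radiographic or bone marrow assessments". Appendix B, footnote a, repeats that response categories and PD "require 2 consecutive assessments made at any time before the institution of any new therapy", and sets no minimum gap.

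On timing, Section 6.4.1 says that serum and urine electrophoresis "are required at screening, on Day 1 of each cycle, and at the EOT Visit". Section 6.2.1 places the End of Treatment (EOT) visit "within 7 days after the decision to permanently discontinue treatment has been made".

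**The concern.** The two DOR definitions start at the same event but name different end dates. The 9.8.3 sentence speaks of documentation for its start and confirmation for its end, so a programmer could fairly take these as different things. Confirmed PD also has a working meaning elsewhere: it is the state that allows pomalidomide and dexamethasone to be added (Section 3.1.1.3) and that separates the later data for analysis (Section 9.1).

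Two analysts could therefore report different DORs from the same data. If the response start is taken as the first qualifying assessment, the literal 9.8.3 reading starts the clock at the first of two assessments and stops it at the second of two. The confirming date cannot precede the first PD date, so any shift lengthens DOR. One subject's DOR could also end after that subject's PFS event as Table 2 defines it.

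**Working it through.** The documents give no expected or median DOR, so there is no stated figure to reproduce. The quantity of interest is

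added DOR = (date of confirming PD assessment) − (date of first PD assessment).

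**Inputs.** Cycle length is 28 days and each visit has a ±3-day window (Section 6.2). Response is assessed on Day 1 of every cycle from Cycle 2 and at EOT (Section 6.4.5). EOT falls within 7 days of the decision to stop (Section 6.2.1) and only after all study treatment has ended (Section 3.2). Radiographic and marrow findings need no second assessment (Section 6.4.5).

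**Gap by route of confirmation.**

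- Next cycle's Day 1: 28 days. With both windows used in full, 28 − 6 = 22 to 28 + 6 = 34 days. A delayed cycle (Section 7.2.4) adds more. This route applies while the subject stays on treatment, for example before pomalidomide and dexamethasone are added.
- EOT visit: time L from first PD assessment to the stop decision, plus up to 7 days. L is not given. Assuming L = 0 to 14 days, the gap runs from about 1 day (L = 0, EOT the next day) to 14 + 7 = 21 days.
- Early repeat sample: less than 28 days.
- Radiographic or marrow PD: 0 days.

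**Average over routes.** The mix of routes is not given. Some assumed mixes, in the order next Day 1 / EOT or early repeat at 7 to 14 days / radiographic or marrow:

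- 100/0/0: 28 days.
- 50/30/20: 0.5 × 28 + 0.3 × 7 = 16.1 days, to 0.5 × 28 + 0.3 × 14 = 18.2 days.
- 20/60/20: 0.2 × 28 + 0.6 × 7 = 9.8 days, to 0.2 × 28 + 0.6 × 14 = 14.0 days.
- 0/80/20: 0.8 × 7 = 5.6 days, to 0.8 × 14 = 11.2 days.

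**Worked subject.** Count days from Cycle 1 Day 1, taken as enrollment. The first of two assessments showing PR is at Cycle 3 Day 1 (2 × 28 = day 56). Laboratory PD is first met at Cycle 8 Day 1 (7 × 28 = day 196) and again at Cycle 9 Day 1 (day 224).

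- Table 2, first-assessment dates: DOR = 196 − 56 = 140 days; PFS = 196 days.
- Section 9.8.3, literal: DOR = 224 − 56 = 168 days, ending 28 days after the Table 2 PFS date.
- Same subject, PD confirmed at an EOT visit 7 days after the first PD assessment: DOR = 203 − 56 = 147 days.
- Both ends dated at confirmation, with response confirmed at Cycle 4 Day 1 (day 84): DOR = 224 − 84 = 140 days. The excess comes from dating the two ends by different rules.

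**Scale.** For an assumed DOR of 3, 6 or 12 cycles (84, 168 or 336 days), with every PD confirmed at the next Day 1, the shift is 28/84 = 33%, 28/168 = 17% and 28/336 = 8%. With a 7-day gap it is 7/84 = 8%, 7/168 = 4% and 7/336 = 2%. The first set is an illustrative ceiling for on-schedule visits, not an expected value.

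**The case against.** The strongest reply is that the texts may not conflict. Section 9.8.3 can be read as the date of a progression that was later confirmed. Alternatively, because a single M-protein rise does not yet meet the PD criterion, Table 2's first documentation may itself mean the second assessment. Under either reading the definitions agree. The protocol defines neither documented nor confirmed. This stands: the discrepancy depends on the literal reading. But no text selects a reading or back-dates PD to its first assessment, so the possibility of two answers remains.

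The same ambiguity affects the response date, since PR or better also needs two assessments. That also stands. A repair to the PD date alone would leave the start of DOR open.

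A reader might infer that time to response plus DOR must equal PFS and that Section 9.8.3 breaks this. The documents do not support that as a requirement. The identity follows from Table 2 only; Section 9.8.2 starts time to response at first dose, while Section 9.8.4 starts PFS at enrollment. Nor do they show a DOR–PFS mismatch within Section 9, because Section 9.8.4 leaves its PD date unspecified. The mismatch appears only against Table 2's PFS definition.

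Finally, DOR is a secondary, descriptive endpoint that may simply be listed, and enrollment has been discontinued. This limits the consequence but does not remove it: subjects with benefit may stay on treatment, and DOR is still to be reported.

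**Conclusion.** The concern holds as an unreconciled date rule. Followed literally, Section 9.8.3 can end DOR later than Table 2 does for laboratory PD that needs two assessments. The difference is nominally 28 days if confirmed at the next Day 1 (22 to 34 with windows), less through EOT or an early repeat, and zero for radiographic or marrow PD.

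This rests on the literal reading of Section 9.8.3 and on taking Table 2's date as the first of the two assessments. The average shift cannot be stated, because the documents give neither the mix of routes nor an expected DOR.

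It would be wrong to infer that every DOR is inflated by 28 days, or that the primary result is affected. The response rate and the Simon stopping and rejection rules do not use the PD date in question, and DOR has no test or comparator. The consequence is a possible modest upward shift, worth correcting because the correction is simple.

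**What to change.** In Section 9.8.3, date both ends of DOR by the same rule. Start at the first of the two consecutive assessments showing PR or better. End at the first documentation of PD, meaning the first of the two consecutive assessments where confirmation is required and the single assessment where it is not. In Section 9.8.4, add one sentence stating that PFS uses the same PD date as DOR for a given subject.

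This is a short rewording of one definition and one added sentence. It needs no new data, because the dates come from response assessments already collected. The downside is that reported DOR may be slightly shorter than under the literal Section 9.8.3 text.

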9.8.4. Progression-free survival (PFS)

Progression-free survival will be calculated as the time between the enrollment and PD, as determined by the investigator using the IMWG criteria, or death, whichever occurred earlier. Subjects who do not have a PFS event will be censored on the last adequate response assessment date. Progression-free survival will be summarized for full analysis population using Kaplan-Meier statistics as appropriate or listed by dose cohort and arm.

9.9. Safety Analysis

All safety analyses will be conducted using the Safety Population. All analyses will be presented by dose cohort and arm.

Adverse events will be coded according to the MedDRA Version 18 or higher. The intensity of AEs will be graded according to the NCI CTCAE Version 4.03 or higher.

Treatment-emergent AEs are defined as AE occurring or worsening on or after the first treatment of the study treatment and within 90 days after last dose of durvalumab. Treatment-emergent AEs, AEs leading to study treatment discontinuation, AEs leading to dose reduction/interruption, AEs related to study treatment, SAEs, and AEs leading to death will be summarized by system organ class, and preferred term for each treatment arm and dose cohort. A summary of AEs with

NCI CTCAE Grade 3 or higher, as well as the most frequent preferred terms, and AESIs will be provided. A summary of AEs by dosing cycle based on onset date will also be provided.

If a subject experiences the same preferred term multiple times then, the event will be counted only once and by greatest severity.

All deaths and reasons for death will be summarized. Deaths within 90 days after the last dose of durvalumab will be summarized separately.

Clinical laboratory values will be graded according to NCI CTCAE Version 4.03 or higher for applicable tests. Baseline grade and worst grade during treatment for selected laboratory results will be summarized. Shift from baseline to the worst grade observed during the treatment for selected laboratory results will also be provided.

For vital signs, shift from baseline to worst during the treatment in below, within, and above the normal ranges will be displayed in cross—tabulations. Summary statistics (N, Mean, Standard Deviation, Median, Minimum, and Maximum) of observed and change from baseline values will be presented.

The overall ECG interpretation will be summarized by presenting the number and percentage of subjects with "Normal", "Abnormal, not clinically significant, and "Abnormal, clinically significant". Shifts from baseline to worst during the treatment in the overall ECG interpretation will be displayed in cross–tabulations.

The number of subjects who develop anti-drug antibody against durvalumab and/or daratumumab will be summarized.

Graphical displays will be provided where useful to assist in the interpretation of results.

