8. CONCOMITANT MEDICATIONS AND PROCEDURES

Over the course of this study, additional medications may be required to manage aspects of the disease state of the subjects, including side effects from trial treatments or disease progression. Supportive care, including but not limited to anti-emetic medications, may be administered at the discretion of the investigator.

See Appendix E for additional details on DURVA toxicity management.

All concomitant treatments, including blood and blood products, used from 28 days prior to first dose of study treatment until 90 days after last dose of DURVA or DARA, whichever is later, must be reported on the eCRF.

For information regarding other drugs that may interact with IP and affect its metabolism, PK, or excretion, please see the IBs and/or local package inserts.

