8.2. Prohibited Concomitant Medications and Procedures

The following medications are considered exclusionary during the study. The sponsor must be notified if a subject receives any of these during the study.

- 1. The prophylactic use of hematopoietic growth factors or platelet/RBC transfusions will not be allowed during the first cycle (DLT evaluation period); however, it is permitted at the Investigator's discretion after a subject completes the first cycle or within the first cycle if a hematological DLT has already been declared for that subject. Subjects who fail absolute neutrophil count, hemoglobin or platelet eligibility criteria at screening should not be retested for the study after being treated with growth factors or platelet/RBC transfusion.
- 2. Any investigational anticancer therapy.
- 3. Any concurrent chemotherapy, radiotherapy (except palliative radiotherapy), immunotherapy, biologic or hormonal therapy for cancer treatment.
- 4. Immunosuppressive medications including, but not limited to systemic corticosteroids at doses exceeding 10 mg/day of prednisone or equivalent, methotrexate, azathioprine, and tumor necrosis factor alpha (TNF-α) blockers. Pre- and post-infusion medication for infusion reaction prophylaxis as outlined in Table 6 is permitted. Use of

immunosuppressive medications for the management of IP-related AEs or in subjects with contrast allergies is acceptable. In addition, use of inhaled, topical, intranasal corticosteroids or local steroid injections (eg, intra-articular injection) is permitted. Temporary uses of corticosteroids for concurrent illnesses (eg, food allergies, CT scan contrast hypersensitivity, moderate to severe infusion-related reactions, etc) are acceptable upon discussion and agreement with the medical monitor.

- 5. Live attenuated vaccines during the study through 30 days after the last dose of durvalumab.
- 6. Herbal and natural remedies are to be avoided.
- 7. Strong inhibitors of CYP1A2 (eg, ciprofloxacin, enoxacin, and fluvoxamine) should be avoided for subjects receiving POM.

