9. STATISTICAL CONSIDERATIONS

9.1. Overview

All analyses will use descriptive statistics. The analyses will be done by cohorts and arms. Subjects treated with the recommended dose in the Phase 2 portion of D^2 will be combined with the corresponding dose cohort in the safety run-in phase as one single dose cohort for efficacy and safety analysis. Safety and efficacy data for subjects after addition of POM + dex following confirmed PD will be analyzed separately.

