All AEs will be recorded by the Investigator from the time the subject signs informed consent until 90 days after the last dose of DURVA or DARA, whichever is later, as well as those SAEs made known to the Investigator at any time thereafter that are suspected of being related to study IPs (durvalumab, daratumumab, POM, dex). Adverse events and SAEs will be recorded on the AE page of the CRF and in the subject's source documents. All SAEs must be reported to Celgene Drug Safety within 24 hours of the Investigator's knowledge of the event by facsimile, or other appropriate method, using the SAE Report Form, or approved equivalent form.

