10.2.3. Causality

The Investigator must determine the relationship between the administration of the IPs (DARA, DURVA, POM, dex) and the occurrence of an AE/SAE as Not Suspected or Suspected as defined below:

Not suspected: A causal relationship of the adverse event to IPs (daratumumab,

durvalumab, POM, dex) administration is **unlikely or remote**, or other medications, therapeutic interventions, or underlying conditions provide a sufficient explanation for the observed

event.

Suspected: There is a **reasonable possibility** that the administration of IPs

(daratumumab, durvalumab, POM, dex) caused the adverse

event. 'Reasonable possibility' means there is evidence to suggest a causal relationship between the IP and the adverse event.

Causality should be assessed and provided for every AE/SAE based on currently available information. Causality is to be reassessed and provided as additional information becomes available.

If an event is assessed as suspected of being related to a comparator, ancillary or additional IP that has not been manufactured or provided by Celgene, please provide the name of the manufacturer when reporting the event.

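### The Section 9.9 treatment-emergent AE window does not stop at a new anti-myeloma therapy, so events on an off-study next regimen enter the all-cause D² safety tables

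*Combined protocol and SAP*

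**What the plan says.** Safety is one of the two primary endpoints. Table 2 (Section 2) describes it as "Type, frequency, seriousness and severity of adverse events (AEs), and relationship of AEs to study treatment".

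Section 9.9 sets the analysis window. A treatment-emergent AE is an "AE occurring or worsening on or after the first treatment of the study treatment and within 90 days after last dose of durvalumab". The window has one end-point, counted from durvalumab. Section 9.9 also counts a repeated preferred term once, at its worst grade, and summarises deaths within 90 days of the last durvalumab dose.

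Section 10.1 has AEs recorded "until 90 days after the last dose of DURVA or DARA, whichever is later". It does not stop recording when a new therapy starts.

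Three other provisions bear on the point:

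- **Section 9.1:** "Safety and efficacy data for subjects after addition of POM + dex following confirmed PD will be analyzed separately".
- **Section 9.9, attribution:** "AEs related to study treatment, SAEs, and AEs leading to death will be summarized by system organ class, and preferred term". Under Section 10.2.3 an event is rated not suspected when, among other reasons, "therapeutic interventions, or underlying conditions provide a sufficient explanation for the observed" event.
- **Section 8.2:** the therapies listed as exclusionary during the study include "Any concurrent chemotherapy, radiotherapy (except palliative radiotherapy), immunotherapy, biologic or hormonal therapy for cancer treatment". The section does not say whether this still applies once a subject has stopped treatment and is only in follow-up.

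**The concern.** Section 9.1 accepts that events after a further regimen is added do not describe D² alone. It applies that principle only to POM + dex given on study. A subject who stops D² and starts a different regimen elsewhere has no equivalent rule, yet stays in the D² window for 90 days after the last durvalumab dose.

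Such subjects are to be expected. Section 3.2 ends treatment at progression or unacceptable toxicity. It allows POM + dex only after at least 2 cycles and at the investigator's discretion. Section 7.2.4 stops all study treatment if durvalumab is permanently discontinued. Section 6.3.1 then continues AE follow-up.

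At stake is how the all-cause tables are read. Cytopenias, infections or deaths on the next regimen would appear in the D² summaries, and no control arm shows the background rate. The worst-grade rule adds to this: a Grade 1 cytopenia on D² that worsens to Grade 4 on the next regimen, within the window, is reported as a Grade 4 treatment-emergent AE.

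**Working it through.** The plan gives no figure for this point, so there is none to reproduce. The check is a reading of the text, followed by arithmetic on stated assumptions.

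**1. Is there a stop at new therapy?** Sections 6.3.1, 8, 9.1, 9.2, 9.9 and 10.1 were read together. None ends the window or AE recording at a new off-study therapy, and no sensitivity analysis does so. The only split is the one in Section 9.1 for on-study POM + dex.

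**2. Which tables are exposed?**

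| Summary in Section 9.9 | Does another provision remove next-regimen events? |
|---|---|
| All treatment-emergent AEs | No |
| Grade 3 or higher | No |
| SAEs | No |
| AEs leading to death; deaths within 90 days | No |
| AEs related to study treatment | Largely, through Section 10.2.3 |
| Any of these after on-study POM + dex | Yes, through Section 9.1 |

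**3. Share of post-dose days on another regimen.** Let g be the days from last durvalumab to next therapy. The share is (90 − g)/90. The document does not give g.

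Durvalumab is given every 28 days (Section 7.2.2.1), and response is assessed on Day 1 of each cycle and at EOT (Section 6.4.5). If progression is confirmed at a scheduled Day 1 visit and that day's durvalumab is not given, about 28 days have passed since the last dose.

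- g = 28: (90 − 28)/90 = 62/90 = 69%.
- g = 56 (first seen at one Day 1 visit and confirmed at the next, with no durvalumab at either; 2 × 28): 34/90 = 38%.

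As a share of the whole window from first dose, with g = 28:

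- Last durvalumab at Cycle 2 Day 1 (day 28): 62/(28 + 90) = 62/118 = 53%.
- Last durvalumab at Cycle 6 Day 1 (5 × 28 = day 140): 62/(140 + 90) = 62/230 = 27%.

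These are shares of days for a subject who switches. They are not event rates.

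**4. Illustration of the effect on a rate.** Let d be the true Grade 3 or higher rate on D², s the share of subjects who start another therapy inside the window, and q the chance of a first Grade 3 or higher event on that therapy inside the window, taken as independent of d. The reported all-cause rate is d + (1 − d)·s·q. All inputs are assumed.

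| d | s | q | Reported rate | Added |
|---|---|---|---|---|
| 40% | 20% | 10% | 0.40 + 0.60 × 0.20 × 0.10 = 41.2% | 1.2 points |
| 40% | 60% | 40% | 0.40 + 0.60 × 0.60 × 0.40 = 54.4% | 14.4 points |
| 60% | 20% | 10% | 0.60 + 0.40 × 0.20 × 0.10 = 60.8% | 0.8 points |
| 60% | 60% | 40% | 0.60 + 0.40 × 0.60 × 0.40 = 69.6% | 9.6 points |

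The spread of 0.8 to 14.4 points shows how far the answer depends on inputs that the document does not contain.

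**The case against.** The strongest reply has four parts.

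- **Section 9.1 already handles POM + dex.** A reader might infer that, because durvalumab continues when POM + dex is added, Section 9.9 pulls the whole four-drug period into the D² tables and contradicts Section 9.1. The text does not support this. Section 9.1 governs how all safety data are partitioned, while Section 9.9 says when an AE is treatment-emergent. An event can meet Section 9.9 and still be reported in the separate POM + dex set. What is missing is a cut date and a cross-reference.
- **Attribution limits the harm.** A reader might infer that next-regimen toxicity is charged to D² throughout the primary safety endpoint. With correct attribution the related-AE table is not affected. The all-cause tables have no such filter, however, and attribution here is an open-label investigator judgement.
- **The exposure figure can be pushed too far.** A 14-day switch would give (90 − 14)/90 = 84%. That fits poorly with 28-day durvalumab dosing and Day 1 response assessment, and would usually need progression found between scheduled visits or treatment stopped mid-cycle. A figure near 69% is a more reasonable upper end.
- **A fixed all-cause window is conservative.** It captures late immune-mediated events whatever is given next. Cutting the main table at new therapy, and keeping later events only if they are AESIs or suspected to be related, would make inclusion depend on causality calls. This objection stands and shapes the fix.

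The analyses are also descriptive. The Cycle 1 DLT rule and the Simon rule on responses do not use these tables, and enrollment has been discontinued. The consequence is limited to reporting and interpretation.

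**Conclusion.** The point holds for subjects who stop D² and start another anti-myeloma therapy within 90 days of their last durvalumab dose. As written, Section 9.9 places events on that therapy in the all-cause treatment-emergent, Grade 3 or higher, SAE and fatal-AE summaries for D². It does not hold for the related-AE table, which is largely protected. For on-study POM + dex the gap is a split that Section 9.9 fails to carry over, not a miscount.

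The effect on AE rates cannot be derived from the document, which does not say how many subjects switch or when. If the switch comes about 28 days after the last durvalumab dose, up to 69% of the post-dose window is on another regimen for that subject. The change is worth making because safety is a primary endpoint with no comparator. The partial clinical hold also concerned a PD-1 antibody combined with IMiDs, so a clear line between D² alone and D² with POM matters for interpretation.

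**What to change.** In Section 9.9:

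1. Keep the full 90-day all-cause treatment-emergent AE table.
2. Add treatment-emergent AE, Grade 3 or higher, SAE and fatal-AE summaries truncated at the earliest of the 90-day limit, the first POM or dex study dose, or the start of any other anti-myeloma therapy.
3. Flag later events, including AESIs, by timing relative to that date, so that none is lost.
4. State that the D² period ends at the first POM or dex study dose, in line with Section 9.1, and say how an event that starts before that date and worsens after it is reported.

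The start date should be recoverable. Section 8 requires reporting on the eCRF of "All concomitant treatments, including blood and blood products, used from 28 days prior to first dose of study treatment until 90 days after last dose". That limit is counted from whichever antibody was given last, so collection covers the whole Section 9.9 window. The sponsor should confirm that sites enter next-line therapy there.

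The cost is one derived date and one extra set of tables.

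The same edit could settle a neighbouring mismatch. The analysis window counts from durvalumab alone, while AE recording runs from the later of the two antibodies. With daratumumab on Day 22 and durvalumab on Day 1 or 2, the last doses in Cycles 1 and 2 can be 22 − 2 = 20 to 22 − 1 = 21 days apart, and AEs recorded in the difference fall outside the definition.
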